# 2. Outcome Measures

52	2.1. Primary outcome measure:
53	The primary outcome measure is patient reported pain on a numeric rating scale (NRS) (1; no
54	pain, 10; worst pain imaginable)
55	
56	2.2. Secondary outcome measures:
57	Patient satisfaction measured on NRS scale of 1=not bad at all, to 10=worst experience
58	imaginable.
59	Analysis of risk factors associated with pain from local anaesthetic in the head and neck
60	including size of resection and injection volume:
61	• Pathology – malignant versus benign
62	Local anaesthetic volume
63	• Size of resection
64	• Site of resection
65	
66	
67	3. Methodological design
68	3.1. Study design
69	Randomized controlled trial
70	
71	3.2. Selection:
72	Patients will be selected from those attending scheduled excision of cutaneous head and neck
73	malignancies at our centre
74	
75	3.3. Inclusion criteria:

76	• Aged at least 18 years
77	• Receiving surgery to cutaneous tissues of the head and neck
78	Procedure performed under local anaesthetic
79	
80	3.4. Exclusion criteria:
81	Paediatric patients
82	• Surgery performed under general anaesthetic
83	• Mucosal operative site (e.g. oral cavity)
84	• Significant cognitive impairment (e.g. severe dementia)
85	Known sensitivity/allergy to EMLA
86	• History of a pain disorder (e.g. complex regional pain syndrome).
87	
88	3.5. Sample size calculation:
89	A formal sample size calculation will be performed after an initial pilot study of ten patients
90	per group to calculate the effect size. Other studies on using topical anaesthetic agents in
91	other non head and neck anatomical sites typically required less than 50 participants per
92	group. G*Power 3.1 (Universität Düsseldorf) software will be used to calculate the necessary
93	sample size. We will likely employ an $\alpha$ error probability of 0.05 and a power of 95%. A 10%
94	margin for safety will be used to mitigate the possible risks of participant attrition
95	
96	3.6. Randomization:
97	Computer randomization will be performed. A random number sequence will be generated
98	using randomizer.org® with numbers allocated using stratified permuted blocks of four and
99	these will be concealed in individual sealed envelopes with the aid of a research contributor.

100	Participants will be allocated in order of recruitment and in participants with more than two
101	lesions will have the more superiorly located lesion allocated first.
102	

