103	3.7. Interventions
104	Patients will be split into 4 groups:
105	• EMLA
106	Aqueous ointment
107	• Ethyl chloride spray
108	• no treatment.
109	
110	3.8. Study procedures
111	Written informed consent will be obtained prior to group allocation. Following group
112	allocation, topical agents will be administered as follows. EMLA (EMLA cream 5% 25g
113	lidocaine, 25g prilocaine) and aqueous cream will be applied to cover the surgical site,
114	delivered via an unmarked syringe to achieve single blinding. A Tegaderm® adhesive
115	dressing will then be applied over this to prevent the cream from drying out, and it will be
116	removed in the theatre before the administration of LA. The local anesthetic to be used will
117	be 1% lidocaine with 1:200,000 adrenaline and will be injected via a 25-gauge needle
118	attached to a 10ml syringe. A 5ml syringe will be occasionally used when it is not possible to
119	inject via a 10ml syringe.
120	EC will be applied to the surgical site before LA injection. The area will be sprayed at a
121	distance of 5-10cm for 4-8 seconds until the skin slightly blanches, and the fluid will be
122	allowed to evaporate.

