### 126 **3.9.**Assessing outcomes

The key focus in this study will be the assessment of pain linked to the injection of local anesthesia (LA). Following the LA administration, each participant will be prompted to evaluate the pain they undergo using a numeric rating scale (NRS; 1=no pain, 10=worst pain imaginable). Subsequent to the procedure, patients will be inquired about their overall perception of the experience (1=not bad at all, 10=worst experience imaginable).

132

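### The multi-lesion rule in 3.6 implies that one participant can receive several arms, which allows carry-over between pain scores, weakens the EMLA versus aqueous blind in those participants, and conflicts with the patient as the unit elsewhere

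*Combined protocol and SAP*

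**What the plan says.** Section 3.6 (Randomization) describes a sequence generated "using randomizer.org® with numbers allocated using stratified permuted blocks of four and" concealed in sealed envelopes. The strata are not named and the allocation ratio is not given. The section continues: "Participants will be allocated in order of recruitment and in participants with more than two" "lesions will have the more superiorly located lesion allocated first". The word 'first' has meaning only if another lesion of the same person is allocated next. Read literally, the rule starts at three lesions, and exactly two lesions are not addressed.

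Elsewhere the unit is the patient. Section 3.5 counts the pilot in patients per group. Section 3.7 says "Patients will be split into 4 groups" and lists EMLA, aqueous ointment, ethyl chloride spray and no treatment. Section 3.9 says that "each participant will be prompted to evaluate the pain they undergo using a numeric rating scale" and then asks for one rating of the overall experience after the procedure.

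Blinding is described in section 3.8 for the two creams only: "delivered via an unmarked syringe to achieve single blinding". For the spray, the text says "EC will be applied to the surgical site before LA injection", with no sham.

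**The concern.** When a block of four holds each of four arms once, consecutive envelopes from that block cannot repeat an arm. A participant whose lesions draw consecutive envelopes will therefore usually receive different arms on the same head and neck. Three things follow.

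- **Carry-over and contrast.** The primary outcome is a subjective rating. The plan fixes the order of allocation but not the order of injection or scoring, and it does not say that pain is scored per lesion. A later score may be given in the light of an injection already received under another arm. For neighbouring lesions it may also be given in skin that the first local anaesthetic has reached. A model for within-patient correlation does not by itself remove this.
- **Blinding.** A participant carrying both EMLA and aqueous cream can compare the two directly. This is the only pair of arms for which blinding is described.
- **The secondary outcome.** One overall-experience score per participant cannot be assigned to an arm when that participant received two or more.

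**Working it through.** The plan states no figure on this point, so there is none to reproduce.

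**Inputs.** Four arms (3.7); permuted blocks of four (3.6). Assumed because not stated: 1:1:1:1 allocation, so each arm appears once per block; all of a participant's lesions in one stratum; and a first lesion equally likely to fall at any of the four block positions.

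**Three lesions, the smallest number the rule literally covers.**
- Mixed arms: three consecutive positions span at most two blocks, so at least two lie in the same block and must differ. Probability 100%. The same holds for four or more.
- Both creams, start at position 1 or 2 (probability 1/2): all three lie in one block. Of the 4 possible sets of three arms, 2 contain both creams: 1/2.
- Both creams, start at position 3 or 4 (probability 1/2): two lesions lie in one block and one in the other. The pair holds both creams with probability 1/6. It holds exactly one cream with probability 4/6, and the single lesion then supplies the other with probability 1/4. Total 1/6 + 4/6 × 1/4 = 1/3.
- Overall: 1/2 × 1/2 + 1/2 × 1/3 = 5/12 = 41.7%.

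**Two lesions, if the rule is applied to them as well.** The pair lies in one block with probability 3/4 and straddles two with probability 1/4.
- Mixed arms: 3/4 × 1 + 1/4 × 3/4 = 15/16 = 93.75%.
- Both creams: 3/4 × 1/6 + 1/4 × 1/8 = 5/32 = 15.6%.
- One lesion with cream, the other without: 3/4 × 2/3 + 1/4 × 1/2 = 62.5%.

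Full enumeration of all 24 × 24 pairs of consecutive blocks and all four start positions gives the same values.

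**Sensitivity: every lesion in a different stratum, so allocations are independent.**
- Mixed arms: two lesions 1 − 4 × (1/4)² = 75%; three lesions 1 − 4 × (1/4)³ = 93.75%.
- Both creams: two lesions 1 − 2 × (3/4)² + (1/2)² = 12.5%; three lesions 1 − 2 × (3/4)³ + (1/2)³ = 28.1%.

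**Trial level.** The share of multi-lesion participants is not stated. Assume that 10% to 50% have exactly two lesions, in one stratum:

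| Share with two lesions (assumed) | All participants with mixed arms | All participants with both creams |
|---|---|---|
| 10% | 0.10 × 15/16 = 9.4% | 0.10 × 5/32 = 1.6% |
| 50% | 0.50 × 15/16 = 46.9% | 0.50 × 5/32 = 7.8% |

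**Is this only a clustering problem?** A null simulation of the Kruskal-Wallis test used 160 patients, 2,000 runs, scores rounded to 1–10, and 30% to 100% of patients with two lesions. Type I error at nominal 0.05 ran from 0.042 down to 0.028 at an assumed within-patient correlation of 0.3, and from 0.039 down to 0.019 at 0.7. Ignoring the pairing is conservative in that setting. The problem here is influence on the scores themselves, which this simulation does not include.

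**The case against.** The strongest reply is that lesion-level allocation is an inference. Section 3.7 divides patients, not lesions, into groups, and section 3.9 has each participant give a score. The documents never say that one person may receive two arms. That is fair. But the rule in 3.6 has no purpose if a participant is allocated only once, and nothing else in the plan says how several lesions are handled. The conflict therefore stands, with mixed arms as the consequence of the more natural reading of 3.6.

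A reader might go further and infer that the rule undoes the single blind. The documents do not support that. The blind is described only for EMLA versus aqueous cream; spray and no treatment are evident to the patient anyway. The 62.5% of two-lesion cases with cream on one site only is therefore not a breach: it may help the patient guess whether the cream worked, but does not show which cream it was. Even a patient with both creams is not told which is which, because the syringes are unmarked, and can only judge by effect. Single-lesion participants are untouched.

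A reader might also infer that the scores are contaminated. The documents say nothing about the spacing of lesions, the spread of local anaesthetic or the sequence of scoring. Contamination is a risk the plan leaves open, not one it demonstrates.

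Finally, allocating different arms within one person is a recognised design. That is true, but it would need per-lesion scoring, a fixed order and a matching analysis. Section 4 plans independent-groups rank tests and has none of these.

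**Conclusion.** The point holds as an unresolved conflict over the unit of allocation, with a foreseeable bias if 3.6 is followed as written. Under equal allocation and a single stratum, mixed arms are certain for three or more lesions and occur in 15/16 of two-lesion participants if the rule extends to them. Lesion-level strata lower this to 75% for two lesions and, if every lesion falls in a different stratum, 93.75% for three. Both creams fall on one person in 41.7% of three-lesion and 15.6% of two-lesion participants in a single stratum.

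The supported consequences are limited to these participants: later pain scores may be influenced by another arm, the blind between the two creams is weakened where both are present, and the overall-experience score cannot be attributed to an arm. The effect on the trial depends on how many participants have several lesions, which the documents do not give. The plan should be changed, since it foresees such participants and the remedy is inexpensive.

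**What to change.** - **Section 3.6:** randomise each participant once. For anyone with two or more lesions, name one index lesion, the most superior, before the envelope is opened. State the allocation ratio and the strata.
- **Section 3.9:** record the index lesion's NRS before any other lesion is injected, and keep other lesions out of the trial comparison. The share of participants with mixed allocation then falls from 93.75% (two lesions) or 100% (three or more) to 0%. The overall-experience score belongs to one randomised arm, although in multi-lesion participants it may still reflect the whole session.
- **If later lesions are kept:** restrict the primary comparison to the first lesion allocated, with the order of injection and scoring fixed before allocation as superior first. Do not define it as whichever lesion happens to be injected first: staff who know the allocations could then determine which arm enters the primary analysis. Pain should be scored per lesion, and any analysis that uses all lesions should account for the participant.

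The cost is the loss of later lesions from the primary comparison (number unknown) and a small constraint on theatre sequence. The rest is wording, and it brings 3.6 into line with the patient-level text in 3.5, 3.7 and 3.9.

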#### 47 **1.2.** Aim

The aim of this study is to assess if ethylene chloride or EMLA are effective in reducing thepain associated with local anaesthetic administration

EMLA and ethyl chloride reduce pain associated with local anaesthetic administration

50

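### The only stated masking covers EMLA versus aqueous cream; every ethyl chloride contrast, and EMLA versus no treatment, is open on a self-scored primary outcome, and no provision masks the injector or the person asking for the score.

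*Combined protocol and SAP*

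**What the plan says.** The hypothesis, printed under 1.2, makes the same claim for both agents: "EMLA and ethyl chloride reduce pain associated with local anaesthetic administration". Neither it nor the aim names a comparator. Section 3.7 sets out the design: "Patients will be split into 4 groups", namely EMLA, an aqueous product, ethyl chloride spray and no treatment.

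Masking appears once, in 3.8. EMLA "and aqueous cream will be applied to cover the surgical site", both "delivered via an unmarked syringe to achieve single blinding". A dressing covers the cream and is taken off in theatre before the injection. The text does not say which single party is blinded.

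For the spray, 3.8 says "EC will be applied to the surgical site before LA injection", continuing "for 4-8 seconds until the skin slightly blanches". No imitation spray is described, and nothing is described for the no-treatment arm.

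The primary outcome (2.1) is the participant's own pain rating from 1 to 10. Under 3.9, after the injection, "each participant will be prompted to evaluate the pain they undergo using a numeric rating scale". The plan does not say who asks, in what words, or whether that person knows the allocation. It also does not say who applies the cream or who injects. The sealed envelopes in 3.6 conceal the allocation before assignment; they do not mask treatment afterwards.

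**The concern.** When participants score their own pain and know what they received, a difference between arms combines the effect of the agent with the effect of knowing. The plan puts the same question to EMLA and ethyl chloride but gives only one of them a comparator that the participant may be unable to tell apart from it. A significant ethyl chloride result would naturally be read as an analgesic effect of cooling, although expectation could produce the same result.

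A second route runs through staff. The injector controls the manner of injection, and 3.8 does not fix its speed or volume. The questioner controls how the score is requested. If either knows the allocation, a gentler injection or a leading prompt could shift scores, even between the two creams.

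Neither weakness can be repaired after data collection, and section 4 does not tell a reader which comparisons were masked.

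**Working it through.** **Step 1: masking by contrast.** Sections 3.7 to 3.9 give:

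| Contrast | What the participant can tell | Masking provided |
|---|---|---|
| EMLA vs aqueous cream | Cream under a dressing in both arms | Unmarked syringe, one party |
| EMLA vs no treatment | Cream or nothing | None |
| Ethyl chloride vs no treatment | Spray or nothing | None |
| Ethyl chloride vs aqueous cream | Spray, or cream under a dressing | None |

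One of the four active-versus-control contrasts has any masking, and no ethyl chloride contrast has any.

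**Step 2: who the single blind covers.** The ordinary reading is the participant. The injector and questioner are then outside the provision. If the one masked party were instead the injector, the participant who gives the score would be unmasked. Either way, the provision leaves at least one person who can influence the score uncovered.

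**Step 3: scale, for illustration.** The plan has no figure to reproduce. Section 3.5 defers the sample size to a pilot of ten per group and gives no effect size or SD. Inputs:

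- two-sided alpha 0.05 (3.5 gives 0.05; two-sided is assumed);
- n = 30 or 50 per arm (assumed; 3.5 says only that studies at other body sites typically needed fewer than 50 per group);
- true effect of the spray zero (assumed);
- shift b in self-report from knowing one was treated: 0.2, 0.3 or 0.5 SD (assumed).

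For a two-sample normal approximation, z = b × √(n/2), and the probability of p < 0.05 is Φ(z − 1.96) + Φ(−z − 1.96).

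| b (SD) | n = 30: z | Probability | n = 50: z | Probability |
|---|---|---|---|---|
| 0 | 0 | 5% | 0 | 5% |
| 0.2 | 0.77 | 12.1% | 1.00 | 17.0% |
| 0.3 | 1.16 | 21.3% | 1.50 | 32.3% |
| 0.5 | 1.94 | 49.1% | 2.50 | 70.5% |

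On the rating scale itself, with 49 per group and SD assumed between 2.5 and 1.5 points, a 0.5-point shift gives 17% to 38% (24% at SD 2). A 1.0-point shift gives 51% to 91% (70% at SD 2).

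Section 4 plans rank tests for non-parametric data, so these z-test figures show the order of magnitude. They are not the trial's own error rates.

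**The case against.** The plan never claims a masked spray comparison: it attaches single blinding only to the creams, so no statement in it is false. That stands; the gap is that the open contrasts are not labelled as such.

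A reader might infer that the plan leaves the injector unmasked as a matter of fact. The documents do not support that. They are silent on who injects, who asks and what those people know, so the supportable statement is that no provision masks them.

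A reader might also call the EMLA comparison half-masked. Against aqueous cream this is too harsh: if the masked party is the participant, the rater is masked, and for a self-reported outcome that is the most valuable protection. Against no treatment it is too generous, because that contrast is fully open.

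Injection is partly standardised in 3.8 (needle, anaesthetic and usual syringe), and 2.2 lists anaesthetic volume as a factor to be analysed. A difference in volume between arms could therefore be seen in the data. A difference in speed or manner could not.

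Finally, the shift and the arm sizes in the illustration have no source in the documents. That is correct, and the figures carry no weight beyond showing that a modest shift matters at plausible arm sizes.

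**Conclusion.** The point holds. Masking is confined to EMLA versus aqueous cream. All ethyl chloride contrasts, and EMLA versus no treatment, are open to the person who scores the primary outcome, and nothing in the plan masks the injector or the questioner. The first part follows directly from 3.7 and 3.8. The second rests on the absence of any provision, not on a statement that these staff know the allocation.

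The concern is greatest for ethyl chloride and smaller for EMLA versus aqueous cream. The size of any bias cannot be derived from the documents. The range of 12% to 70% applies only under an assumed 0.2 to 0.5 SD shift, 30 to 50 per arm and no true effect; it should not be read as this trial's false-positive rate. A change before recruitment is worthwhile because it is cheap and cannot be made later.

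**What to change.** 1. **Section 3.8.** Keep participant masking to cream type and say explicitly that the participant is the masked party. Add that the injector and the person asking for the score are not told which cream was used. Have someone other than the injector handle the prepared unmarked syringe and apply the cream, drawn from existing staff where possible.
2. **Section 3.9.** Request the score with one fixed, scripted sentence, identical in all four arms.
3. **Section 4.** Name EMLA versus aqueous cream as the masked contrast. State that the ethyl chloride contrasts and EMLA versus no treatment are open-label, and that conclusions from them cannot separate a drug or cooling effect from expectation.
4. **Optional.** Report aqueous cream minus no treatment descriptively, as a cream-based indication of the effect of attention and expectation. It must not serve as a correction for spray expectation: participants given aqueous cream do not know whether theirs is active, spray participants know what they received, and the cream arm also includes a dressing.

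The cost is protocol wording and minor theatre coordination. The plan does not say that different people apply the cream and inject, and 5.2 foresees no funding, so a compulsory split into three roles is not proposed. The injector and questioner may still be able to tell spray, cream and no treatment apart. The ethyl chloride claim becomes more modest.

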### 126 **3.9.**Assessing outcomes

The key focus in this study will be the assessment of pain linked to the injection of local anesthesia (LA). Following the LA administration, each participant will be prompted to evaluate the pain they undergo using a numeric rating scale (NRS; 1=no pain, 10=worst pain imaginable). Subsequent to the procedure, patients will be inquired about their overall perception of the experience (1=not bad at all, 10=worst experience imaginable).

132

## 133 4. Statistical analysis

The distribution pattern of variables will be assessed using the Kolmogorov-Smirnov test. 134 The Kruskal-Wallis test and Mann Whitney test will be employed to compare groups for non-135 parametric data and for covariate analysis. The Chi-squared test will be applied to detect 136 differences for categorical data. Spearman's Rho will be used to quantify the strength of the 137 138 linear relationship between non-parametric continuous variables. A per protocol analysis will be conducted as it is believed that in cases where patients are unable to describe their pain by 139 using a number, it will disproportionately affect the results by conducting a "worst case 140 141 scenario" analysis. Furthermore, due to a minimal interval between intervention and measurement of pain outcomes in this study, there will be low rates of attrition. Statistical 142 analysis will be performed using SPSS v.26 (Aramonk, US). Statistical significance will be 143 144 considered at p < 0.05.

145

- 146
- 147
- 148

149

150	5. Miscellaneous
151	5.1. Ethical considerations:
152	This trial will be registered with the University Hospital Waterford Research and Ethics
153	Committee where full ethical approval will be obtained prior to study commencement. It
154	is considered that patient risks from this study are negligible.
155	
156	5.2. Funding:
157	No funding will be necessary for this study
158	
159	5.3. Dissemination of results
160	Results will be prepared into a scientific manuscript for publication and presented at

161 scientific surgical meetings

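### Section 4 compares the arms with unadjusted rank tests only; adjusting for lesion site, which the plan already lists as a suspected driver of pain, could recover some efficiency at little cost

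*Combined protocol and SAP*

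**What the plan says.** - **Arm comparison (section 4).** "The Kruskal-Wallis test and Mann Whitney test will be employed to compare groups", and the same sentence extends both tests to non-"parametric data and for covariate analysis". Chi-squared is assigned to categorical data. For continuous variables, "Spearman's Rho will be used to quantify the strength of the" relationship between pairs of variables. No regression, ordinal, stratified or other multivariable method is named for any outcome.
- **Covariates (section 2.2).** The secondary outcomes include "Analysis of risk factors associated with pain from local anaesthetic in the head and neck", "including size of resection and injection volume". The list covers pathology, anaesthetic volume, size of resection and "Site of resection". The number of site categories and the time at which size is recorded are not given.
- **Design (sections 3.5 to 3.7).** "Patients will be split into 4 groups". Blocks of four are described as stratified, but no strata are named. The sample size is to be calculated after a pilot of ten per group, probably at alpha 0.05 and 95% power. The plan gives no N, effect size, SD or covariate-outcome correlation.

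**The concern.** The plan treats lesion site as something that may affect injection pain, but uses it only in one-at-a-time association tests. The label of covariate analysis does not change this: a Kruskal-Wallis or Mann-Whitney test of pain across sites says whether site and pain are associated, and leaves the treatment contrast as it was.

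If site does predict pain, its share of the variance stays in the error term of the primary comparison. The trial then needs more patients for a given power, or has less power for a given number. Site is fixed before treatment and will be recorded anyway, so this information can be used almost free of charge.

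**Working it through.** **No plan figure to reproduce.** The plan states no sample size or effect size. Everything below is illustrative, and R2 (the share of pain variance explained by the adjusting covariate) is assumed throughout.

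**1. If the trial is sized for 95% power.** Inputs: 95% power and alpha 0.05 from section 3.5, two-sided testing assumed, and 50 per arm assumed as a round upper benchmark.

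Detectable standardised difference: d = (1.960 + 1.645) × sqrt(2/50) = 3.605 × 0.2 = 0.72.

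Adjustment multiplies the residual SD by sqrt(1 − R2). Power at 50 per arm is then Φ(3.605/sqrt(1 − R2) − 1.960), and n per arm for unchanged power is 50 × (1 − R2), rounded up.

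| R2 | SE ratio | Power at 50 per arm | n per arm for 95% power |
|---|---|---|---|
| 0 | 1.000 | 95.0% | 50 |
| 0.05 | 0.975 | 95.9% | 48 |
| 0.10 | 0.949 | 96.7% | 45 |
| 0.20 | 0.894 | 98.1% | 40 |
| 0.30 | 0.837 | 99.1% | 35 |

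For R2 of 0.1 to 0.3 the gain is 1.7 to 4.1 power points, or 10 to 30% fewer patients.

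**2. If the trial has less power than that.** Simulated scenario (all assumed): four arms, 45 per arm, a 0.6 SD shift, five site groups and a score rounded to 1–10. The adjusted analysis is a linear model on ranks with arm, site and a size term that has no effect.

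| R2 for site | Mann-Whitney | Site-adjusted rank model | Gain (points) |
|---|---|---|---|
| 0 | 0.78 | 0.78 | 0 |
| 0.1 | 0.77 | 0.81 | 4 |
| 0.2 | 0.77 | 0.85 | 8 |
| 0.3 | 0.76 | 0.89 | 13 |

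Type I error of the adjusted model was 0.045 to 0.054. Separate two-arm runs of the same scenario gave 0.78 vs 0.77, 0.78 vs 0.81, 0.77 vs 0.84 and 0.77 vs 0.88, which are gains of −1, 3, 7 and 11 points. Taken together, about 4, 8 and 12 points is a fair summary. At R2 = 0.05 a rerun gave 0.77 for both analyses.

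**3. Cost of estimating the covariate terms.** With N patients, k = 4 arms and p covariate terms, variance inflates by 1 + p/(N − k − p − 1). The break-even R2 is 1 − 1/inflation.

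- Site in five groups (p = 4), N = 200: 1 + 4/191 = 1.021, break-even 0.02.
- Site plus size (p = 5), N = 200: 1 + 5/190 = 1.026, break-even 0.03.
- Site (p = 4), the 40 pilot patients: 1 + 4/31 = 1.129, break-even 0.11.
- Site plus size (p = 5), the 40 pilot patients: 1 + 5/30 = 1.167, break-even 0.14.

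**4. Choice of adjusted model.** A proportional-odds model with arm and site (two arms, 45 per arm) had power of 0.78, 0.82, 0.86 and 0.90 at R2 of 0, 0.1, 0.2 and 0.3. Its Wald test had type I error of 0.054 to 0.064. In a four-arm version with site and size at R2 = 0.2, Wald type I error was 5.8% at 45 per arm and 9.0% at ten per arm. The likelihood-ratio version was not simulated.

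**The case against.** The strongest reply is that nothing here is wrong. A rank test between randomised arms is valid whether or not site is in the model, and its type I error already allows for chance differences in site mix. That stands. A reader might infer that the planned comparison is biased, or that chance imbalance in site invalidates it. The documents do not support this: imbalance adds random error, which the test accounts for. If site turned out to be one of the unnamed strata, even that imbalance would largely disappear.

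Three further objections also stand, and they limit the point:

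- **R2 is not evidenced.** Listing site as a risk factor to be analysed poses a question. It does not show that site explains 10 to 30% of the variance.
- **The trial is not shown to be underpowered.** Section 3.5 mentions 95% power, and at that level the gain is small in power terms. The figure of under 50 per group in section 3.5 describes other studies at other body sites; it is not this trial's expected size.
- **Pre-allocation lesion size is not stated as collected.** Section 2.2 lists size of resection, a surgical quantity with no stated timing. Only site clearly qualifies as a baseline covariate.

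The objection that the ordinal model may misbehave in small samples also holds for the Wald test, and most of all at pilot size. It bears on how to adjust in the main trial, and is not a reason to leave site out.

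**Conclusion.** The point holds as a matter of efficiency. Section 4 names no method that can adjust the treatment contrast, and site is a pre-treatment variable that the plan itself suspects of affecting pain.

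The size rests on an assumed R2. It is negligible at 0.05 or below. At 0.1 to 0.3 it is about 4 to 12 power points with 45 per arm and a 0.6 SD shift, or about 2 to 4 points if the trial is sized for 95% power, equivalent to about 10 to 30% fewer patients. If site explains nothing, the loss is about 0 to 2 points. The possible gain outweighs this small, bounded cost, so the change is worth making before the sample size is fixed. It is not a condition for the trial's validity.

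**What to change.** In section 4:

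1. Name the primary treatment contrasts, which the plan does not do at present.
2. Estimate them in the main trial from one four-arm model adjusted for site, with a few site groups fixed in advance. Use either a linear model on ranks or a proportional-odds model tested by likelihood ratio rather than Wald. Check the chosen test's type I error by simulation at the final sample size.
3. Keep Kruskal-Wallis and Mann-Whitney as supporting analyses.
4. Add planned lesion size only if it is recorded before allocation. Leave injected volume out, because it is determined after allocation.
5. Do not apply the adjusted model to the ten-per-group pilot alone.

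The cost is one paragraph of text and a short list of site groups, plus one baseline measurement if size is included. Statistically, it is a few degrees of freedom if site does not predict pain, and mildly inflated type I error if a proportional-odds Wald test is used in small samples.
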